7.2 Participant Discontinuation/Withdrawal from the Study

The participant's parent or guardian may withdraw voluntarily from participation in the study at any time. The participant's parent or guardian is not obligated to state the reason for withdrawal. The reasons for withdrawal, or failure to provide a reason, must be documented by the investigator on the completion/ withdrawal section of the electronic case report form (CRF). We will also document missing values in the database for subjects who withdraw from the study.

An investigator may discontinue or withdraw a participant from the study for the following reasons:

- If any clinical AE, laboratory abnormality, or other medical condition or situation occurs such that continued participation in the study would not be in the best interest of the participant
- Disease progression which requires discontinuation of the study intervention
- If the participant meets an exclusion criterion (either newly developed or not previously recognized) that precludes further study participation (e.g., prescribed a second anti-epileptic drug for seizures)

7.3 Lost to Follow-up

A participant will be considered lost to follow-up if he or she fails to return for developmental follow-up at 18-24 months and is unable to be contacted by the study site staff.

The following actions must be taken if a participant fails to return to the clinic for a required study visit:

- The investigator or coordinator will attempt to contact the participant and reschedule the missed visit and counsel the participant's parent or guardian on the importance of

maintaining the assigned visit schedule and ascertain if the parent or guardian wishes to and/or should continue in the study.

- Should the participant continue to be unreachable, he or she will be considered to have withdrawn from the study with a primary reason of lost to follow-up.

8 STUDY ASSESSMENTS AND PROCEDURES

8.1 Study Procedures

8.1.1 Screening/Baseline

Research staff will screen for eligibility requirements. After the parent or guardian has provided informed consent and after it has been determined that the participant satisfies all inclusion and no exclusion criteria, the following evaluations will be recorded in the CRF:

1. Participant demographics
 - a. Maternal race/ethnicity
 - b. Maternal age
 - c. Inborn/outborn
 - d. Infant sex
 - e. Gestational age (weeks)
 - f. Postnatal age (hours)
2. Neurological exam
 - a. Level of consciousness
 - i. Hyperalert or irritable
 - ii. Lethargic or poorly responsive
 - iii. Minimal or no responsiveness
 - b. Spontaneous activity
 - i. Slightly decreased
 - ii. Decreased
 - iii. Absent
 - c. Posture
 - i. Mild distal flexion
 - ii. Distal flexion, complete extension
 - iii. Decerebrate
 - d. Tone
 - i. Hypertonic
 - ii. Hypotonic
 - iii. Flaccid
 - e. Primitive Reflexes
 - i. Suck
 1. Normal
 2. Weak or bite
 3. Absent
 4. Unable to assess
 - ii. Moro
 1. Low threshold to elicit
 2. Weak or incomplete
 3. Absent
 4. Unable to assess
 - f. Autonomic

- i. Pupils
 - 1. Equal and reactive
 - 2. Constricted
 - 3. Dilated and either fixed or sluggishly reactive; asymmetric
 - 4. Unable to assess
- ii. Respiration
 - 1. Normal
 - 2. Periodic breathing
 - 3. Intubated or ventilated
- 3. Birth weight (grams)
- 4. Medical history
 - a. All Apgar scores (0-10)
 - b. Chest compressions in the delivery room (yes/no)
 - c. Lowest pH among cord arterial, cord venous, and arterial blood gas taken before 1 hour of age
 - d. Sentinel event, defined as placental abruption, shoulder dystocia, uterine rupture, or prolapsed cord
 - e. Severity of encephalopathy based on Sarnat staging³ (mild, moderate, or severe)
 - f. Start time of therapeutic hypothermia
- 5. Respiratory support at time of enrollment (room air, oxyhood, nasal cannula/CPAP, or mechanical ventilation) and maximum FIO₂ exposure during each 24-hour period
- 6. Concomitant medications (see Section 6.5)
- 7. Laboratory evaluations (see Section 8.2.1)

8.1.2 Treatment

The first dose of caffeine must be given prior to 24 hours postnatal age. The day of the first caffeine dose will be considered study day 1, with subsequent doses given 24 hours apart on study day 2 and 3. During this treatment period, the following evaluations will be recorded in the CRF:

- 1. Date, time (start time, stop time, and flush time), and dose of each caffeine administration
- 2. Daily weight (grams)
- 3. Highest respiratory support (room air, oxyhood, nasal cannula/CPAP, or mechanical ventilation) and maximum FIO₂ exposure during each 24-hour period
- 4. Concomitant medications (see Section 6.5)
- 5. Laboratory evaluations (see Section 8.2.1)
- 6. Urine output (in mL/kg/hour)
- 7. PK sampling (date and time) (see Section 8.2.2)
- 8. Epigenetic sampling (date and time) (see Section 8.2.2)
- 9. Clinical events of interest: death, sepsis, disseminated intravascular coagulopathy, hypotension, hypertension, hepatic dysfunction, acute kidney injury, persistent pulmonary hypertension, and thrombocytopenia.
- 10. Adverse events (see Section 8.3), including seizures requiring > 1 AED and NEC

11. Head imaging results (including cranial ultrasounds and head computed tomography [CT], if obtained per standard of care, and brain MRI) (see Section 8.1.6)

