1.2 Schema

1.3 Schedule of Activities (SoA)

	Screen/ Baseline	Treatment	Follow-up Period	Discharge/Transfer /Death	Final study assessment
Time point	< 24 hours postnatal age	Study day 1-3	7 days following last caffeine dose		18-24 Months
Informed consent	X				
Demographics	X				
Neurological Exam	X			X	X
Weight	X	X	X	X	X
Medical history	X				X ¹
Respiratory Support	X ²	X ²	X ²	X	
Laboratory evaluations ³	X	X	X		
Urine output	X	X	X		
Caffeine administration ⁴		X			
Concomitant medications		X	X		
Adverse events ⁵		X	X		
PK sampling ⁶		X	X		
Epigenetic sampling ⁷		X	X		
Clinical events of interest ⁸		X	X		
Head imaging ⁹		X	X	X	
Hearing screen				X	
Surgical procedures		X	X	X	
Bayley-III composite scores and GMFCS					X

¹ Follow-up visit will include information on hearing impairment requiring hearing aids, blindness, and cerebral palsy diagnosis. ² Highest respiratory support (room air, oxyhood, nasal cannula/CPAP, or mechanical ventilation) and maximum FIO₂ exposure during each 24-hour period. ³ See Section 8.2.1. ⁴ Includes exact start, stop, and flush times for all caffeine doses. ⁵ Seizures requiring > 1 anti-epileptic drug and necrotizing enterocolitis are adverse events of special interest. ⁶ Date and time for each sample. ⁷ Obtained from scavenged blood samples, if available. ⁸ Includes death, sepsis, disseminated intravascular coagulopathy, hypotension, hypertension, hepatic dysfunction, acute kidney injury, persistent pulmonary hypertension, and thrombocytopenia. ⁹ Includes cranial ultrasounds and head CT, if done per standard of care, and brain MRI.

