2.3 Risk/Benefit Assessment

2.3.1 Known Potential Risks

Risks of Blood Drawing

There are small risks to blood sampling, usually some pain/discomfort with the blood stick and blood loss. Every effort will be made to avoid additional (to standard of care) sticks for this study and will time clinical blood draws to coincide with timed samples, using existing intravenous lines when possible. A maximum of 7 plasma PK samples per participant will be collected during the treatment and follow-up periods. PK blood samples will be obtained only if laboratory tests are being collected per routine medical care. Each sample will be limited to a volume of 250 μ L. The expected total maximum amount will be no more than 1.75 mL (about 1/3 of a teaspoon).

Caffeine⁵¹

1. Published literature reports have raised questions regarding possible association between the use of methylxanthines, such as caffeine, and the development of necrotizing enterocolitis (NEC) in premature neonates, although a causal relationship has not been established.^{52,53}
2. Caffeine is a central nervous system stimulant and in cases of caffeine overdose, seizures have been reported.⁵⁴
3. Caffeine increases heart rate and should be used with caution in neonates with cardiovascular disease.
4. Caffeine should be used with caution in neonates with impaired renal or hepatic function.

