2.3.3 Assessment of Potential Risks and Benefits

Given the high incidence of mortality and NDI in neonates with HIE, we propose that the value of the information to be gained in this study outweigh the potential risks of exposure to caffeine. We have minimized these potential risks by using a dose of caffeine that is equivalent to the dose ranges used on-label for apnea of prematurity in preterm neonates. We will exclude neonates with difficult to control seizures (i.e., receiving > 1 anti-epileptic drug [AED]), tachycardia (defined as heart rate > 180 beats per minute for > 4 hour), or major congenital anomalies, including congenital heart disease. We will collect data on seizures and necrotizing enterocolitis as safety events of interest. We will review safety data prior to dose escalation between cohorts.

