8.1.3 Follow-up Period

The following assessments will be recorded in the CRF for the follow-up period (7 days following the final dose of caffeine):

1. Daily weight (grams)
2. Highest respiratory support (room air, oxyhood, nasal cannula/CPAP, or mechanical ventilation) and maximum FIO₂ exposure during each 24-hour period
3. Concomitant medications (see Section 6.5)
4. Laboratory evaluations (see Section 8.2.1)
5. Urine output (in mL/kg/hour)
6. PK sampling (date and time) (see Section 8.2.2)
7. Epigenetic sampling (date and time) (see Section 8.2.2)
8. Clinical events of interest: sepsis, disseminated intravascular coagulopathy, hypotension, hypertension, hepatic dysfunction, acute kidney injury, persistent pulmonary hypertension, and thrombocytopenia.
9. Adverse events (see Section 8.3), including seizures requiring > 1 AED and NEC
10. Head imaging results (including cranial ultrasounds and head CT, if obtained per standard of care, and brain MRI) (see Section 8.1.6)

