9.4.4.1 Clinical Definitions

1. Sepsis- Positive blood culture and ≥ 7 days of antibiotic treatment
2. Disseminated Intravascular Coagulopathy: Transfusion of platelets, fresh frozen plasma, or cryoprecipitate
3. Hypotension: Requiring inotrope or vasopressor support
4. Hypertension: Requiring antihypertensive medication
5. Hepatic dysfunction: AST > 200 IU/L or ALT > 100 IU/L
6. Acute Kidney Injury (AKI), stage 1-3 classified using Kidney Disease: Improving Global Outcomes (KDIGO) system (**Table 5**). We will use the highest serum creatinine per 24-hour period. A participant will be assigned a stage if they meet either serum creatinine or urine output criteria listed below.

Table 5. AKI KDIGO Classification⁶¹

Stage	Serum Creatinine (SCr)	Urine Output
0	No change in SCr or rise <0.3 mg/dL	≥ 1.0 mL/kg/hour
1	SCr rise ≥ 0.3 mg/dL within 48 hours or SCr rise ≥ 1.5 - $1.9 \times$ reference SCr ^a within 7 days	> 0.5 and ≤ 1 mL/kg/hour

2	SCr rise \geq 2.0-2.9 X reference SCr ^a	> 0.3 and \leq 0.5 mL/kg/hour
3	SCr rise \geq 3 X reference SCr ^a or SCr \geq 2.5 mg/dL or receipt of dialysis	\leq 0.3 mL/kg/hour

^aReference SCr will be defined as the lowest previous SCr value

7. **Persistent Pulmonary Hypertension**: Requiring inhaled nitric oxide and fraction of inspired oxygen >0.50
8. **Thrombocytopenia**: Platelet count $< 100,000$ per μL
9. **Seizures** will be defined by the receipt of > 1 AED, as we are interested in identifying seizures which are difficult to control.
10. **Necrotizing Enterocolitis** - Bell Stage II or III⁵⁷

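### Raised heart rate is a named caffeine risk, but after entry the plan has no tachycardia definition, no heart-rate record and no solicited collection of it

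*Combined protocol and SAP*

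**What the plan says.** Section 2.3.1 lists four risks of caffeine. The third is "Caffeine increases heart rate and should be used with caution in neonates with cardiovascular disease". Section 2.3.3, describing how risk is kept down, excludes infants with "tachycardia (defined as heart rate > 180 beats per minute for > 4 hour"; section 5.2, item 2, applies the same limit at entry.

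The safety events collected after entry are set out in several places:
- Section 8.1.2, item 9 (treatment): "Clinical events of interest: death, sepsis, disseminated intravascular coagulopathy, hypotension, hypertension, hepatic dysfunction, acute kidney injury, persistent pulmonary hypertension, and thrombocytopenia".
- Section 8.1.3, item 8 (follow-up): "Clinical events of interest: sepsis, disseminated intravascular coagulopathy, hypotension, hypertension, hepatic dysfunction, acute kidney injury, persistent pulmonary hypertension, and thrombocytopenia". This is the same list without death.
- Schedule of Activities, footnote 8: "Includes death, sepsis, disseminated intravascular coagulopathy, hypotension, hypertension, hepatic dysfunction, acute kidney injury, persistent pulmonary hypertension, and thrombocytopenia".
- Section 2.3.3: "We will collect data on seizures and necrotizing enterocolitis as safety events of interest". Section 8.3.8 defines these two and no others as events of special interest.
- Section 9.4.4.1 gives ten clinical definitions. Its haemodynamic entries are hypotension, hypertension and persistent pulmonary hypertension, each defined by treatment given; hypotension, for example, is "Requiring inotrope or vasopressor support".

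Alongside these lists there is general AE reporting. Section 8.3.1 counts a clinical change as an AE when the investigator considers it clinically significant. Section 7.1 requires new clinically relevant findings to be reported as AEs, section 8.3.4 requires all AEs to be documented whether or not related, and section 9.4.1 tabulates them by cohort and MedDRA term.

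**The concern.** The protocol regards raised heart rate as an effect of the study drug and treats sustained tachycardia as serious enough to bar entry. One would expect the same quantity to be followed once dosing starts. It is not. There is no vital-signs or heart-rate row in the Schedule of Activities, no heart-rate item in the baseline, treatment or follow-up CRF lists, and no tachycardia entry among the solicited events or definitions.

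Two uses of the data are affected. The independent safety monitor reviews cohort 1 (9 infants) before the higher maintenance dose is opened, and for this risk would have only the reports that investigators chose to make. The final by-cohort safety tables would rest on the same reports, made without a shared threshold by staff who know the dose. A difference between cohorts in those tables, or its absence, could reflect reporting habits as much as the drug.

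**Working it through.** No figure in the plan depends on this point, so there is nothing to reproduce. The check is a reading of every data-collection list, followed by an illustration with assumed values.

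**Step 1. Named risks against collected events**

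| Risk in section 2.3.1 | Event followed after dosing | Where defined |
|---|---|---|
| NEC | Bell stage II or III, special interest | 8.3.8, 9.4.4.1 |
| Seizures | More than one AED, special interest | 8.3.8, 9.4.4.1 |
| Increased heart rate | None | Nowhere |
| Caution with impaired renal or hepatic function | AKI (KDIGO stage); hepatic dysfunction (AST or ALT limit) | 9.4.4.1 |

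**Step 2. The two measurable exclusions side by side**

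| | More than one AED | Sustained tachycardia |
|---|---|---|
| Entry exclusion (5.2) | Yes | Yes |
| Risk-minimisation step (2.3.3) | Yes | Yes |
| Given as the withdrawal example (7.2) | Yes | No |
| Event of special interest (8.3.8) | Yes | No |
| Clinical definition (9.4.4.1) | Yes | No |

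The protocol gives no reason for following one after entry and not the other.

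**Step 3. What general AE reporting can and cannot supply**
- It supplies tachycardia that an investigator judges significant, with onset, severity and resolution.
- It supplies no common threshold, since section 8.3.1 leaves significance to judgement.
- It supplies no baseline. Section 8.3.4 treats conditions present at screening as baseline and counts only deterioration as an AE, but section 8.1.1 records no heart rate against which deterioration could be shown.
- It does not support an analysis of measured heart rate against caffeine exposure. Section 9.4.4 plans to correlate exposure with seizures and NEC only. Yet section 9.1 expects clearance at least 20% lower than usual. At a fixed dose AUC = dose / CL, so a 20% fall means AUC higher by a factor of 1 / 0.80 = 1.25 or more, which makes a known drug effect more relevant here.

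**Step 4. Illustration of incomplete capture in cohort 1**

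Input from section 4.1: n = 9. Assumed, because the documents give neither: the true proportion p of infants with tachycardia, and the share c of those who are reported. With infants independent,

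P(at least one reported) = 1 − (1 − p·c)^9.

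For p = 0.20 and c = 0.5: 1 − 0.90^9 = 0.61.

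| p | c = 1 | c = 0.5 | c = 0.25 |
|---|---|---|---|
| 10% | 0.61 | 0.37 | 0.20 |
| 20% | 0.87 | 0.61 | 0.37 |
| 30% | 0.96 | 0.77 | 0.50 |

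Halving the capture has the same effect as halving the true rate. The review is weakened but not emptied.

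**The case against.** The strongest reply is that the AE system already covers this. AEs are a CRF item in both the treatment and follow-up periods, the definition is open, and a tachycardia that mattered clinically would be documented, tabulated and available to the monitor. That is correct. A reader might infer from the event lists that no tachycardia would be collected at all; sections 7.1, 8.3.1, 8.3.4 and 9.4.1 do not support that reading. What they leave open is definition, completeness and a baseline.

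A reader might also infer that the pre-escalation review could miss a difference between the cohorts. It cannot, because it takes place before cohort 2 enrols and sees cohort 1 only. Comparison of the cohorts belongs to the final tables, and no test between cohorts is planned.

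Section 7.2 adds little. It lets the investigator withdraw an infant who newly meets an exclusion criterion "If the participant meets an exclusion criterion (either newly developed or not previously recognized) that precludes further study participation". That is a discretionary bedside decision made from the medical record and needs no research field.

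It is also fair to say that the risk is partly handled at entry, by excluding congenital heart disease and sustained tachycardia; that blood-pressure events are solicited; that recorded concomitant medications would show drug-treated rhythm problems; and that section 3 explains the choice of seizures and NEC as events of special interest. Safety is a secondary objective, behind clearance. All of this stands and limits the weight of the point. None of it provides a heart-rate record after dosing.

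Finally, the limit in section 5.2 was written for eligibility, and nothing in the documents validates it as an on-treatment endpoint. That is a reason to use it for recording only and to keep the daily value beside it.

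**Conclusion.** The point holds in a limited form. For one of the four caffeine risks that the protocol names, the plan has no prespecified event definition, no systematic heart-rate record (including at baseline) and no solicited collection. The monitor's review of cohort 1 and the final by-cohort tables therefore depend, for this risk, on investigator-judged AE reports without a common threshold, in an open-label trial at up to 3 sites.

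This is a gap in the quality of secondary safety data. It does not contradict another part of the plan, and it does not affect the clearance endpoint or any sample-size figure. The documents do not let its size be estimated. The probabilities above rest on assumed rates, assumed reporting shares and independence between infants, and show only the direction and the plausible scale of the loss. The change is worth making because it is cheap and brings this risk into line with the other three.

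**What to change.** - Add sustained tachycardia to the clinical events of interest in section 8.1.2 item 9, section 8.1.3 item 8 and Schedule of Activities footnote 8, and to the definitions in section 9.4.4.1. Use the wording already in sections 2.3.3 and 5.2, and state that it serves as a recording definition only.
- Record the highest charted heart rate per 24-hour period at baseline, during treatment and during follow-up, taken from routine NICU monitoring, with a matching row in the Schedule of Activities.
- Tabulate both by cohort in the safety analysis, and include the cohort 1 data in what the independent safety monitor reviews before cohort 2 opens.

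The cost is one added definition, one more event on an existing list and one daily field from routine charting: a small data-entry burden with no extra procedure for the infant. No dose, withdrawal or stopping rule is proposed.

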8.1.3 Follow-up Period

The following assessments will be recorded in the CRF for the follow-up period (7 days following the final dose of caffeine):

1. Daily weight (grams)
2. Highest respiratory support (room air, oxyhood, nasal cannula/CPAP, or mechanical ventilation) and maximum FIO₂ exposure during each 24-hour period
3. Concomitant medications (see Section 6.5)
4. Laboratory evaluations (see Section 8.2.1)
5. Urine output (in mL/kg/hour)
6. PK sampling (date and time) (see Section 8.2.2)
7. Epigenetic sampling (date and time) (see Section 8.2.2)
8. Clinical events of interest: sepsis, disseminated intravascular coagulopathy, hypotension, hypertension, hepatic dysfunction, acute kidney injury, persistent pulmonary hypertension, and thrombocytopenia.
9. Adverse events (see Section 8.3), including seizures requiring > 1 AED and NEC
10. Head imaging results (including cranial ultrasounds and head CT, if obtained per standard of care, and brain MRI) (see Section 8.1.6)

8.1.4 Discharge/Transfer/Death

At the time of the participant's discharge from the hospital, transfer, or death, the following assessments, when available, will be recorded in the CRF:

1. Head imaging results (including cranial ultrasounds and head CT, if obtained per standard of care, and brain MRI) (see Section 8.1.6)
2. Hearing screen results (pass or referred)
3. Neurological exam
 - a. Normal
 - b. Moderate; any abnormal findings such as mild head lag
 - c. Severe; significant neurological abnormalities, such as:
 - i. Increased peripheral tone
 - ii. Poor suck
 - iii. Marked head lag
4. Surgical procedures during hospitalization
 - a. Gastrostomy tube
 - b. Tracheostomy
 - c. Peritoneal drain
 - d. Abdominal laparotomy
 - e. Inguinal hernia repair
 - f. Neurosurgical procedure
 - g. Other
5. Respiratory support

8.1.5 Final Study Assessment

At the follow-up visit at 18-24 months, the following assessments will be recorded in the CRF:

1. Head imaging results (if obtained following discharge)
2. Neurological exam
 - a. Normal
 - b. Moderate; any abnormal findings
 - c. Severe; significant neurological abnormalities
3. Bayley-III composite scores
 - a. Cognitive
 - b. Language
 - c. Motor
4. Gross Motor Function Classification System scores
5. Medical history
 - a. Cerebral palsy diagnosis
 - b. Hearing impairment requiring hearing aids
 - c. Blindness

8.2 Safety and Other Assessments

Safety will be assessed through the neonate's initial hospitalization and it will be assessed by frequency and incidence of AEs and SAEs.

8.2.1 Laboratory Evaluations

All infants receiving therapeutic hypothermia for HIE receive laboratory evaluations per unit guidelines. An example of this lab schedule used at UNC is shown in **Table 4**. Following completion of therapeutic hypothermia, there are no guidelines at UNC, so additional labs are obtained per discretion of the clinician. We will define abnormal lab values using reference ranges used in the Pediatric Trials Network.⁵⁶ We will record the following labs during the baseline, treatment, and follow-up periods:

1. Arterial blood gas: We will record the temperature-corrected pH, PCO₂, PaO₂, and base deficit/excess on blood gases obtained every 12 hours during the treatment period and then daily, if available, during the follow-up period. If blood gases are drawn more frequently than daily, we will use the blood gas with the lowest pH for that day. If an arterial blood gas is not available, we will record venous/capillary gases, if available.
2. For serum chemistry (chem 10): sodium (mmol/L), potassium (mmol/L), Blood Urea Nitrogen (BUN) (mg/dL), creatinine (mg/dL), bicarbonate (mmol/L), calcium (mg/dL), chloride (mmol/L), magnesium (mg/dL), phosphorus (mg/dL), and glucose (mg/dL).
3. For CBC with differential: white blood cell count, hematocrit, and platelet count..
4. For liver function tests: AST (U/L), ALT (U/L), Albumin (g/dL), Alkaline phosphatase (U/L), Gamma-glutamyl Transferase (GGT) (U/L)
5. For Neobili: Total bilirubin, direct bilirubin (mg/dL).
6. For coagulation studies: Prothrombin time (PT) (seconds), partial thromboplastin time (PTT) (seconds), international normalized ratio (INR), and fibrinogen (mg/dL).
7. Microbiology: Cultures from sterile body fluids

Table 4. Laboratory Evaluation Schedule for Therapeutic Hypothermia at UNC

LABORATORY EVALUATION SCHEDULE						
All hours refer to hours post start of cooling, not hours of life						
HOUR 0	HOUR 12	HOUR 24	HOUR 36	HOUR 48	HOUR 60	HOUR 72
* Blood gas (If not previously obtained)	Blood gas (POC or lab gas) iCa Glucose	Blood gas (POC or lab gas) iCa Glucose	Blood gas (POC or lab gas) iCa Glucose	Blood gas (POC or lab gas) iCa Glucose	Blood gas (POC or lab gas) iCa Glucose	Blood gas (POC or lab gas) iCa Glucose
Chem 10	Chem 10	Chem 10		Chem 10		Chem 10
CBC with differential		CBC with differential		CBC with differential		
	Neobili	Neobili		Neobili		Neobili
Liver Function Tests AST ALT Total Protein Albumin Total bilirubin Direct bilirubin Alk Phosphatase GGT		Liver Function Tests AST ALT Total Protein Albumin Total bilirubin Direct bilirubin Alk Phosphatase GGT				Liver Function Tests AST ALT Total Protein Albumin Total bilirubin Direct bilirubin Alk Phosphatase GGT
Coagulation Studies PT PTT INR Fibrinogen		Coagulation Studies PT PTT INR Fibrinogen				

* For blood gas results, always look at the temperature corrected values.

